17.5.2. ECG POTENTIALLY CLINICALLY SIGNIFICANT CRITERIA

Potentially clinically significant ECG measurements will be identified in accordance with the following predefined PCS criteria:

Table 3: Predefined ECG PCS criteria.

ECG Parameter	PCS Low	PCS High
Heart Rate (beats/min)	--	≥ 100
PR Interval (msec)	--	≥ 210
QRS Interval (msec)	--	≥ 120

17.6. VITAL SIGNS

The following vital sign measurements will be reported for this study:

- Supine and Standing Systolic Blood Pressure (mmHg)
- Supine and Standing Diastolic Blood Pressure (mmHg)
- Supine and Standing Pulse Rate (bpm)
- Respiratory Rate (breaths/min)
- Temperature ($^{\circ}\text{C}$)
- Height (cm)
- Weight (kg)

Document: PPD

Author: PPD

Version Number:

1.0

Version Date:

06MAY2024

- BMI (kg/m²)
- Waist Circumference (cm)

Height will be summarized as part of the Baseline characteristics only.

The following summaries will be provided:

- By-visit summary with 95% CI of the mean of observed values and change from Baseline values for vital sign measurements, including Week 9/Follow-up/Visit 11.
- Number and percentage of subjects with at least one PCS vital sign value (see [Section 17.6.2](#)) post Baseline. The period of evaluation includes both the treatment period and the follow-up period, including unscheduled visits. Subjects will be counted in a particular PCS category if they met that PCS criteria at least once post Baseline, regardless of their Baseline value.
- Number and percentage of subjects with orthostatic hypotension and/or orthostatic tachycardia (see [Section 17.6.1](#)). The data will be summarized for Baseline and the overall post-Baseline period (which covers both the treatment period and the follow-up period, including unscheduled visits), as well as by visit, including Week 9/Follow-up/Visit 11.
- By-visit summary of BMI category (see [Section 7.5](#)) and shift in BMI category from Baseline to each post-Baseline time point.
- By-visit summary with 95% CI of the mean of observed values and change from Baseline values for vital signs measurements by BMI category (see [Section 7.5](#)).

All vital signs data will be provided in a data listing. In addition, a separate listing will be generated to present the vital signs data that met the PCS criteria. All occurrences of orthostatic hypotension and orthostatic tachycardia will also be presented in a listing.

Boxplots will be created to present weight data by time point and treatment group. The boxplots will be repeated to present the change from Baseline values.

17.6.1. VITAL SIGN SPECIFIC DERIVATIONS

- BMI expressed in kg/m² = Weight (kg)/ height (m)².

Document: PPD

Author: PPD

Version Number:

1.0

Version Date:

06MAY2024

The height collected at Visit 1 will be used to derive BMI where needed throughout the study.

- Orthostatic hypotension is defined as a decrease of ≥ 20 mmHg in systolic blood pressure or ≥ 10 mmHg in diastolic blood pressure after a subject has been standing for at least 2 to 4 minutes, compared to the systolic blood pressure and diastolic blood pressure measured in the supine position, respectively.
- Orthostatic tachycardia is defined as a heart rate increase of ≥ 20 bpm after a subject has been standing for at least 2 to 4 minutes compared to the heart rate measured in the supine position, and a heart rate of > 100 bpm after the subject has been standing for at least 2 to 4 minutes.

17.6.2. VITAL SIGN POTENTIALLY CLINICALLY SIGNIFICANT CRITERIA

Potentially clinically significant vital sign measurements will be identified in accordance with the following predefined PCS criteria:

Table 5: Predefined vital sign PCS criteria.

Vital Sign Parameter	PCS Low	PCS High
Systolic Blood Pressure (Supine, Standing) (mmHg)	Value ≤ 90 and ≥ 20 decrease from Baseline	Value ≥ 180 and ≥ 20 increase from Baseline
Diastolic Blood Pressure (Supine, Standing) (mmHg)	Value ≤ 50 and ≥ 15 decrease from Baseline	Value ≥ 105 and ≥ 15 increase from Baseline
Pulse Rate (Supine, Standing) (beats/min)	Value ≤ 50 and ≥ 15 decrease from Baseline	Value ≥ 120 and ≥ 15 increase from Baseline
Weight (kg)	$\geq 7\%$ decrease from Baseline	$\geq 7\%$ increase from Baseline
Temperature (°C)	NA	Value $\geq 38.3^{\circ}\text{C}$ and $\geq 0.8^{\circ}\text{C}$ increase from Baseline

17.7. PHYSICAL EXAMINATION

As all physical and neurological findings will be recorded as medical history or AEs, no specific analysis of physical and neurological Document: PPD

Author: PPD

Version Number:

1.0

Version Date:

06MAY2024

examination will be performed.

17.8. OTHER SAFETY ASSESSMENTS

17.8.1. COLUMBIA SUICIDE SEVERITY RATING SCALE (C-SSRS)

The C-SSRS is a tool designed to systematically assess and track suicidal behavior and suicidal ideation for lifetime, one month prior to the screening visit for suicidal ideation and 6 months prior to the screening visit for suicidal behavior, and throughout the study. The strength of this suicide classification system is in its ability to comprehensively identify suicidal events while limiting the over-identification of suicidal behavior. The C-SSRS Baseline/Screening Version is used at the screening visit and the C-SSRS Since Last Visit Version is used from Visit 2 and onward. Subjects with Type 4 (active suicidal ideation with some intent to act, without specific plan) or Type 5 (active suicidal ideation with specific plan and intent) suicidal ideation during the study will be discontinued from the study and referred to a mental health professional.

C-SSRS includes two main sections: Suicidal Ideation and Suicidal Behavior.

The following outcomes are C-SSRS categories and have binary responses (yes/no). The categories are re-ordered from the scale to facilitate the definitions of the C-SSRS endpoints, and to provide clarity in the presentation of the results.

- Suicidal ideation is measured by 5 categories, representing 5 subtypes of suicidal ideation with increasing severity:
 - Category 1: Wish to be Dead
 - Category 2: Non-specific Active Suicidal Thoughts
 - Category 3: Active Suicidal Ideation with Any Methods (Not Plan) without Intent to Act
 - Category 4: Active Suicidal Ideation with Some Intent to Act, without Specific Plan
 - Category 5: Active Suicidal Ideation with Specific Plan and Intent
- Suicidal behavior is measured by 5 categories, representing 5 subtypes of suicidal behavior:
 - Category 6: Preparatory Acts or Behavior
 - Category 7: Aborted Attempt
 - Category 8: Interrupted Attempt
 - Category 9: Actual Attempt (non-fatal)
 - Category 10: Completed Suicide

Document:

PPD

Author:

PPD

Version Number:

1.0

Version Date:

06MAY2024

The 10 categories above are not mutually exclusive. Subjects will be counted in each category for which they have an event.

Self-injurious behavior without suicidal intent is a non-suicide-related C-SSRS outcome, and also has a binary response (yes/no).

For the purpose of C-SSRS analysis, “Baseline” and the overall “post-Baseline” periods are defined as follows.

Time point	Study Visit	C-SSRS Version	Derivation Rule
Baseline	Visit 1	Baseline/Screening – Past 1 Month for Suicidal Ideation / Past 6 Months for Suicidal Behavior	Most severe outcome
	Visit 2*	Since Last Visit	
Post-Baseline	All post-Baseline visits up to and including Visit 10 (the follow-up visit), including unscheduled visits	Since Last Visit	Most severe outcome

* Note: The Visit 2 C-SSRS assessment must be administered prior to the first dose of study medication in order to be used in the C-SSRS Baseline derivation.

The following C-SSRS composite endpoints will be derived for each time point of interest (i.e., Baseline, overall post-Baseline, and each scheduled visit including Week 9/Follow-up/Visit 11) as follows:

- Any suicidal ideation: A “yes” answer to any one of the 5 suicidal ideation questions on C-SSRS (Categories 1-5).
- Any suicidal behavior: A “yes” answer to any one of the 5 suicidal behavior questions on the C-SSRS (Categories 6-10).
- Any suicidality: A “yes” answer to any one of the 10 suicidal ideation and behavior questions on the C-SSRS (Categories 1-10).

For each subject, the suicidal ideation score at each time point of interest (i.e., Baseline, overall post-Baseline, the LOCF endpoint, and each scheduled visit including Week 9/Follow-up/Visit 11) is defined as the maximum suicidal ideation category (1-5) present for the time point of interest. If no ideation is present a score of 0 is assigned.

The number and percentage of subjects with any suicidality, any suicidal ideation and subtypes of ideation, any suicidal behavior and subtype of

Document: PPD

Author: PPD

Version Number:

1.0

Version Date:

06MAY2024

behavior, and any non-suicidal self-injurious behavior will be presented for:

- Baseline (as defined above)
- The overall post-Baseline period (as defined above)
- Each scheduled visit: Screening/Visit 1 (lifetime; past 1 month for ideation/past 6 months for behavior), Pre-switch Baseline/Visit 2, Week1/Visit 3, Week2/Visit 4, Week 3/Visit 5, Week 4/Visit 6, Week 5/Visit 7, Week 6/Visit 8, Week 7/Visit 9, Week 8/Visit 10 and Week 9/Follow-up/Visit 11.

Shift in suicidal ideation score from Baseline to the overall post-Baseline period, to each of the scheduled visits (Week1/Visit 3, Week2/Visit 4, Week 3/Visit 5, Week 4/Visit 6, Week 5/Visit 7, Week 6/Visit 8, Week 7/Visit 9, Week 8/Visit 10 and Week 9/Follow-up/Visit 11), and to the LOCF endpoint will be presented.

Intensity of ideation for the most severe ideation subtype is measured in terms of frequency, duration, controllability, deterrents, and reasons for ideation. Each is measured with responses ranging from 1 to 5 for frequency and duration, and from 0 to 5 for controllability, deterrents, and reasons for ideation. The ideation intensity total score is the sum of responses to the five items and can range from 2 to 25 for subjects with endorsed suicidal ideation. For subjects with endorsed suicidal ideation, if one or more of these five items are missing at an assessment, the total score will be set to missing. If a subject did not endorse any suicidal ideation, a score of 0 for the ideation intensity total score will be given.

Actual lethality associated with actual attempts is rated on a 6-point scale from 0 = 'No physical damage or very minor physical damage' to 5 = 'Death'. Potential lethality of actual attempts (if actual lethality = 0) is rated on a 3-point scale from 0 = 'Behavior not likely to result in injury' to 2 = 'Behavior likely to result in death despite available medical care'.

Responses to each C-SSRS question will be listed. The ideation intensity total score and the actual lethality and potential lethality of actual attempts will only be presented in data listings.

Document: PPD

Author: PPD

Version Number:

1.0

Version Date:

06MAY2024

17.8.2. ABNORMAL INVOLUNTARY MOVEMENT SCALE (AIMS)

The AIMS is a clinician-rated assessment of abnormal movements consisting of unobtrusive observation of the subject at rest (with shoes removed) and several questions or instructions directed toward the subject. It contains seven items related to: facial, lip, jaw, and tongue movements (items 1 - 4), upper and lower extremity movements (items 5 - 6), and trunk movements (item 7). Three other items assess the subject at a global level (items 8 - 10), and two items assess dental status (items 11 - 12).

The (non-global) AIMS total score is the sum of items 1 through 7. (Items 8 through 12 are not used in AIMS total score calculation.) The possible range for AIMS total score is 0 to 28. Higher values of the AIMS total score indicate increased severity in abnormal movement. If one or more of the 7 items contributing to AIMS total score calculation are missing at a visit, the total score will be set to missing for that visit.

AIMS total score at each visit is classified as 'abnormal' if: either at least two items (out of items 1 - 7) have a response of 'Mild' or higher (i.e., item score ≥ 2); or at least one item (out of items 1 - 7) has a response of 'Moderate' or higher (i.e., item score ≥ 3). Otherwise, the non-missing AIMS total scores is classified as 'normal'.

Item 8 of AIMS represents the global severity score. Post-Baseline AIMS global severity scores will be classified as 'worsened', 'unchanged', or 'improved', relative to a subject's Baseline response to item 8. A higher score than that of the Baseline would be classified as 'worsened'. Conversely, a lower score would be classified as 'improved'. If the score is equal to that of Baseline, the score will be classified as 'unchanged'.

AIMS is assessed at these study visits: Visit 2 and Visit 10.

The observed AIMS total score and the change from Baseline values will also be summarized descriptively by treatment group and visit. In addition, the observed AIMS total score and the change from Baseline values will be summarized descriptively by the subgroups of concomitant medication use for treatment of movement disorders.

Shift from Baseline in AIMS total score category (Normal/Abnormal) to each post-Baseline scheduled visit (Week 8/Visit 10) and to the overall post-Baseline period (including both the treatment period and the follow-up period) will be summarized descriptively by treatment group.

The observed AIMS global severity score and the change from Baseline values will be summarized descriptively by treatment group and visit. In addition, the frequency distribution of the AIMS global severity item will be summarized descriptively by treatment group and visit. Post-Baseline changes in AIMS global severity score (Worsened/Unchanged/Improved) will also be summarized descriptively by treatment group and visit.

17.8.3. BARNES AKATHISIA RATING SCALE (BARS)

The BARS is a rating scale geared toward assessment of neuroleptic-induced akathisia, though it can be used to measure akathisia associated with other drugs as well. The BARS consists of four items, including one item assessing objective restlessness (item 1), two items targeting subjective

Document: PPD

Author: PPD

Version Number:

1.0

Version Date:

06MAY2024

restlessness (awareness and related distress; items 2 - 3), and one global clinical assessment of akathisia item (item 4). The objective and subjective items are anchored and utilize a 4-point scale. The global assessment item has a 6-point scale (from absence of akathisia through severe akathisia).

The BARS total score is the sum of items 1 through 3 and ranges from 0 to 9. Higher values of the BARS total score indicate higher severity of akathisia. If one or more of items 1 to 3 are missing at a visit, the BARS total score will be set to missing for that visit.

The post-Baseline BARS Global Clinical Assessment of Akathisia responses will be classified as 'worsened', 'unchanged', or 'improved', relative to a subject's Baseline response to this item. A higher score than that of the Baseline would be classified as 'worsened'. Conversely, a lower score would be classified as 'improved'. If the score is equal to that of Baseline, the score will be classified as 'unchanged'.

BARS is assessed at these study visits: Visit 2 and Visit 10.

The observed BARS total score and the change from Baseline values will also be summarized descriptively by treatment group and visit. In addition, the observed BARS total score and the change from Baseline values will be summarized descriptively by the subgroups of concomitant medication use for treatment of movement disorders.

Post-Baseline changes in BARS global clinical assessment score (Worsened/Unchanged/Improved) will be summarized descriptively by treatment group and visit.

Lastly, the observed BARS item scores and the change from Baseline values will be summarized descriptively by treatment group and visit. In addition, the frequency distribution of each BARS item will be summarized descriptively by treatment group and visit.

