- j. BMI will be calculated and recorded in the eCRF by the clinical site at screening. For other visits, BMI will be derived in the EDC system.
- k. Subjects must be fasted (no food or drink except water at least 8 hours prior to specified blood tests) at Pre-switch Baseline (Visit 2) and Week 8/EOT/ET (Visit 10). Fasting for 8 hours prior to Screening (Visit 1) is also recommended to avoid potential retests. Blood samples should be drawn in the morning followed by a snack or meal. A list of clinical laboratory tests is provided in [Section 23](#).
- l. Blood samples for follicle stimulating hormone (FSH) will be collected for post-menopausal women or if menopause is suspected.
- m. Any positive urine β -hCG test should be confirmed by a serum β -hCG test.

C [REDACTED] **C** [REDACTED] Blood samples for determination of plasma SEP-363856 concentrations will be collected predose (prior to administration of the first dose) on Day 1; 3 additional samples will be collected on Days 8, 29 and 57/ET. The time and date of the previous dose of study drug and the time and date of blood sampling must be recorded. The remaining plasma samples, after PK measurement is completed, **CCI** [REDACTED].

- p. Positive urine drug screen (UDS) results should be discussed with the Medical Monitor.
- q. Unscheduled SAS, BARS and AIMS scales should be administered if a subject develops extrapyramidal symptoms (EPS) requiring treatment.
- r. Healthcare resource utilization questions are described in [Section 11.5.8](#). Baseline will have 3-month lookback period. Week 8/ET will be since last assessment.
- s. Events occurring prior to first dose of study drug are pretreatment events. Events occurring after first dose of study drug are adverse events. Determination done programmatically.
- t. Where local regulations allow, duplicate subject check will be performed. Following the last contact with a subject, the duplicate enrollment system should be updated, as appropriate.

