10.1.2. Pre-switch Antipsychotic Taper

The pre-switch antipsychotic is held stable for the first week. Beginning on Day 8, the Investigator can start to taper pre-switch antipsychotic and has discretion to complete the taper by end of Week 2, 3, 4, 5, or 6. See [Section 21 Appendix II](#) for guidelines for pre-switch antipsychotic taper.

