6.4. RETESTS, UNSCHEDULED VISITS, AND EARLY TERMINATION DATA

In general, for by-visit summaries, data recorded at the planned visits where assessment is intended to be given will be presented, as well as the derived Baseline value and the LOCF value.

Unscheduled measurements will not be included in by-visit summaries as a separate time point. Unscheduled measurements collected prior to the first dose of study medication will contribute to the derivation of the Baseline value. Unscheduled measurements collected post Baseline will contribute to the derivation of the LOCF value, the potential clinically significant (PCS) value, and the best/worst case value where required (e.g., shift table).

In the case of a retest, the assessment recorded under the planned visit will be used for by-visit summaries, and the assessment(s) recorded under unscheduled visit(s) will be presented in listings only.

As per protocol, study Visit 10 can be a Week 8/End of Treatment (EOT) visit or an Early Termination (ET) visit. If a subject terminates early, his/her measurements taken at the ET visit will be mapped to the next planned visit (after the last scheduled visit the subject attended) during which that assessment was expected to be performed as specified by the Schedule of Assessments table in the protocol. This applies to both safety and effectiveness data.

Listings will include scheduled, unscheduled, retest and early discontinuation data with original dates and visits displayed.

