17.8.4. SIMPSON-ANGUS SCALE (SAS)

The SAS is a clinician-rated assessment of neuroleptic-induced Parkinsonism consisting of 10 items. Items are anchor-based, rated on a 5-point scale (ranging between 0 and 4), and address rigidity, gait (bradykinesia), tremor, akathisia, shoulder shaking, glabellar tap, and salivation.

SAS mean score is defined as the average of all 10 items and ranges between 0 and 4. Lower values of the SAS mean score indicate milder symptoms. If one or more of the SAS items are missing at a visit, the SAS mean score will be set to missing for that visit.

The SAS mean score at each visit will be classified as 'abnormal' if it exceeds 0.3 (Rush, et al., 2000). Otherwise, the non-missing SAS mean score will be classified as 'normal'.

SAS is assessed at these study visits: Visit 2 and Visit 10.

The observed SAS mean score and the change from Baseline values will also be summarized descriptively by treatment group and visit. In addition, the observed SAS mean score and the change from Baseline values will be summarized descriptively by the subgroups of concomitant medication use for treatment of movement disorders.

Document: PPD

Author: PPD

Version Number:

1.0

Version Date:

06MAY2024

Shift from Baseline in SAS mean score category (Normal/Abnormal) to each post-Baseline scheduled visit (Week 8/Visit 10) and to the overall post-Baseline period (including both the treatment period and the follow-up period) will be summarized descriptively by treatment group.

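### Unscheduled BARS ratings reach no BARS summary table when a scorable Visit 10 or early-termination rating follows, so akathisia that settles before Week 8 is missing from that endpoint's tables

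*SAP*

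**What the plan says.** **Schedule.** SAP 17.8.3: "BARS is assessed at these study visits: Visit 2 and Visit 10". Protocol Table 2 agrees.

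**Taper.** Under Protocol 10.1.2 the pre-switch antipsychotic is held for the first week. From Day 8 the investigator may taper it and "has discretion to complete the taper by end of Week 2, 3, 4, 5, or 6".

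**Extra ratings.** Protocol Table 2, footnote q: "Unscheduled SAS, BARS and AIMS scales should be administered if a subject develops extrapyramidal symptoms (EPS) requiring treatment".

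**Handling of extra ratings.** SAP 6.4: "Unscheduled measurements will not be included in by-visit summaries as a separate time point". The same section says that by-visit tables show "data recorded at the planned visits where assessment is intended to be given will be presented, as well as the derived Baseline value and the" carried-forward (LOCF) value. After Baseline, unscheduled values may feed the LOCF value, the potentially clinically significant (PCS) value "and the best/worst case value where required (e.g., shift table").

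**BARS tables.** SAP 17.8.3 summarizes total score, item scores and item frequencies by visit. It also gives total score by use of medication for movement disorders. For the global item: "Post-Baseline changes in BARS global clinical assessment score (Worsened/Unchanged/Improved) will be summarized descriptively by treatment group and visit".

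**Sister scales.** The SAS category (Normal/Abnormal) is shifted from Baseline to Week 8 and also "to the overall post-Baseline period (including both the treatment period and the follow-up period) will be summarized descriptively by treatment group" (SAP 17.8.4). SAP 17.8.2 gives the AIMS total score category the same treatment.

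**The concern.** Change from Baseline in the BARS is a listed endpoint (Protocol 6.3), and the cross-taper is the part of the study in which a switch-related movement problem might be expected to show. EPS medicines are also being withdrawn in that window (Protocol 10.3.4). Footnote q gives the trial a way to rate such an episode when it happens. If the rating then reaches no table, the BARS results describe only the state at the end of Week 8, or at early termination.

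For completers, the Visit 10 rating follows at least two weeks on study drug alone (Protocol 7.3.1). It may also be taken while the subject is on propranolol, which Protocol 10.3.4 permits for akathisia. The BARS tables could therefore report no worsening while the database holds ratings, prompted by the protocol, that recorded it.

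**Working it through.** The plan states no figure on this point, so there is none to reproduce. The check follows one unscheduled BARS rating through the SAP's rules.

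**1. Can it fall in the taper?** Yes. The taper runs from Day 8 to the end of Week 6 at the latest (about Day 43). The scheduled ratings are on Day 1 and Day 57. In a completer, 57 − 43 = 14 days separate the latest taper end from the only scheduled post-Baseline rating.

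**2. Can it enter a by-visit table?** No. SAP 6.4 excludes it as a time point.

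**3. Can it enter LOCF?** Only if it is the last rating with a BARS total score up to and including Visit 10 (SAP 6.3). A scorable Visit 10 rating displaces it. So does an early-termination rating, which SAP 6.4 maps to Visit 10 for this scale. A rating after Visit 10 cannot enter LOCF at all.

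**4. Can it enter a PCS table?** No. The SAP sets no such criterion for BARS.

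**5. Can it enter a worst-case table?** SAP 6.4 allows this only where an analysis calls for it. SAP 17.8.3 has no shift table, no worst value and no overall post-Baseline period. The medication-subgroup summary adds none.

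**Worked case (hypothetical subject).**

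| | Baseline | Week 3, unscheduled | Visit 10 |
|---|---|---|---|
| BARS total (0–9) | 0 | 6 | 0 |
| Global item (0–5) | 0 | 4 | 0 |

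- Week 8, current plan: total change 0 − 0 = 0; global Unchanged.
- LOCF, current plan: the Visit 10 rating is used, so again 0 and Unchanged.
- Worst post-Baseline global value: 4 − 0 = +4; Worsened.

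Without a scorable Visit 10 or early-termination rating, the Week 3 value would become the LOCF value and the subject would show as Worsened there.

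**Comparison with AIMS and SAS.** Both are scheduled at the same two visits, and neither is scheduled at the follow-up visit. Their overall post-Baseline row can therefore differ from the Week 8 row only through unscheduled ratings. Footnote q ratings thus have a route into a table for two of the three scales, but not for the BARS.

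**Size.** The documents give no rate of treated EPS or akathisia. All that can be said is the weight of one hidden episode: with 101 enrolled (SAP 3.4), and if all had a post-Baseline BARS, 1/101 = 1.0%.

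**The case against.** The strongest reply is that the SAP does what the protocol asks. Protocol 15.3.5.9 calls for the motor scales by visit and at the Week 8 LOCF endpoint, and leaves further analyses to the SAP as needed. That stands: this is not a departure from the protocol.

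Other replies also carry weight:

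- **The episode is not lost to the report.** If recorded as an adverse event, akathisia is tabulated by SOC and preferred term with maximum severity (SAP, AE severity section) and again in the extrapyramidal table. Treatment for it appears among the concomitant medications, and the rating itself is listed. A reader might infer that such akathisia would be invisible in the study report. The documents do not support that; it would be absent only from the BARS tables.
- **The parallel with AIMS and SAS is partial.** Their overall-period tables are Normal/Abnormal shifts built on stated cut-offs. The SAP gives BARS no cut-off, and AIMS global severity, the nearest match to the BARS global item, is also summarized by visit only. Nor do those shifts capture akathisia, which need not cross an AIMS or SAS threshold.
- **The trigger is softer than it may look.** Footnote q says should, and names EPS. Protocol 10.3.4 mentions EPS and akathisia separately, so it is not explicit that akathisia alone prompts a BARS. That the footnote prescribes the BARS points towards inclusion, but does not settle it.
- **Ascertainment is unequal.** Extra ratings should arise mainly in subjects with treated EPS; the others have one post-Baseline rating. A mean change to the maximum total score would mix the two. This bears on the choice of fix.

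None of these gives an unscheduled BARS rating a way into a BARS table when a scorable Visit 10 or early-termination rating follows it.

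**Conclusion.** The gap is real and narrow. Under SAP 6.3, 6.4 and 17.8.3, an unscheduled BARS followed by a scorable Visit 10 or early-termination rating enters no BARS summary table. An episode that has returned to Baseline by then is counted as Unchanged, and its rating is found only in a listing. Episodes still present at Visit 10 or early termination are tabulated.

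This rests on reading SAP 6.4 as written, with worst-case values used only where a section requires them, and on sites performing the footnote q ratings. How many subjects are affected cannot be estimated from the documents. The BARS is a descriptive endpoint outside the primary and secondary set in a single-arm study, so neither of those endpoints is touched. A cheap improvement is warranted.

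**What to change.** In SAP 17.8.3, for the BARS Global Clinical Assessment, add a Worsened/Unchanged/Improved count (or a shift table) from Baseline to the worst value in the overall post-Baseline period. Include unscheduled ratings, and present it beside the Week 8 and LOCF results. No cut-off is needed, because the three categories are already defined there.

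Add a footnote that extra ratings occur only in subjects with treated EPS, so ascertainment is unequal. For the same reason, do not add a mean change to the maximum total score.

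Cost: SAP wording and one descriptive table from data already planned for collection, with no new assessment. The downside is that the added table can only look the same as or less favourable than the Week 8 table, which is why it should sit beside that table with the footnote.
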